# **8** Analysis plans for secondary endpoints:

- Rate- or proportion-based endpoints: Several measures will be evaluated in patients that will be summarized as incidence rates or the proportion of patients who have an event or incident of interest; e.g., mortality within 14 days. For these endpoints, we will calculate the proportions of patients who have these incident events of interest for each of the treatment arms and calculate 95% confidence intervals for these outcomes. These will be graphically and quantitatively compared using chi-square tests. Logistic regression models will be used to assess the influence of treatment arm on the incidence of these events while adjusting for other factors of interest.
- Time-to-event endpoints: Similarly, several measures will be analyzed in a secondary manner that will evaluate the distributions of the time to events of interest. These include time to hospital discharge, survival, or symptom improvement. For these outcomes, Kaplan-Meier methods will be used to graphically evaluate potential differences between treatment arms or other groups of interest. Further, these methods will be used to estimate median times as well as time-specific rates (*e.g.*, rate of transfer to hospital at 14 days). Cox proportional hazards models will be used to evaluate the influence of treatment arms, adjusting for other factors of interest.

- Oxygen supplementation and intubation: We will assess the incidence of oxygen supplementation or intubation and time to initiation of oxygen supplementation or intubation. In those who are given oxygen supplementation, we will summarize the duration of oxygen supplementation. Similarly, we will characterize and summarize the need for and duration of intubation. These will be analyzed in a manner similar to that described for the proportion/rate-based variables as well as the time-to-event variables but will specifically be based on a subset of patients given the nature of the outcome of interest. As such, these evaluations will be exploratory in nature.
- Influence of demographic factors on outcomes: These endpoints of interest will tie in with earlier stated analyses, where we will overall assess how these demographic factors such as age, biological sex, and race and ethnicity may influence the outcomes. Since this study will be done at multiple different nursing homes that see different races and ethnicities of patients, these analyses can help to assess if there are any differential outcomes or interactions with factors on these outcomes.
- Senescent cell markers: The distribution of changes in the senescent cell markers will be summarized graphically stratified by treatment arms. Differences between the groups will be assessed using linear regression analysis at the time of interest, adjusting for baseline values. Mixed effects models, where feasible, will also be used to assess the treatment affect using all available measurements.

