### 1.1 Background

**Coronavirus-19 (CoV):** Coronaviruses constitute the subfamily *Orthocoronavirinae*, in the family *Coronaviridae*, order *Nidovirales*, and realm *Riboviria*. They are enveloped viruses with a positive-sense single-stranded RNA genome and a nucleocapsid of helical symmetry. They are the largest among known RNA viruses. As of December 22, 2020, there have been at least 1.71 million confirmed deaths and more than 77.6 million confirmed cases in the β-coronavirus-19 (CoV) pandemic. CoV can cause physical dysfunction (frailty) and death from hyperinflammation, cytokine storm, and associated acute respiratory distress syndrome (ARDS), myocarditis with troponin leak, and multi-organ failure, particularly in older or chronically-ill individuals, with 25-50% of nursing home residents who test positive (PCR) dying from CoV complications.

Cellular Senescence: Senescent cells were discovered in 1961 when serially-subcultured human embryonic fibroblasts were shown to lose replicative capacity, yet remain viable. This prompted work to test if aging leads to accumulation in vivo of pre-senescent cells, which have limited remaining replicative potential, and senescent cells, which cannot replicate but are metabolically active. Senescent cell burden is very low in young individuals but increases with aging in several tissues, including adipose tissue, lung, skeletal muscle, heart, kidney, brain, bone, and skin. For example, we found the number of primary adipocyte progenitors (preadipocytes) with limited replicative potential (pre-senescent and senescent cells) cloned from adipose tissue of rats that were isogenic and raised under controlled conditions rises across the age spectrum^6. Cellular senescence contributes to age-related dysfunction and multiple diseases throughout the lifespan. Senescent cells appear at pathogenic sites of many major diseases, including in the lung in chronic lung disease, asthma, smoking, and idiopathic pulmonary fibrosis (IPF), adipose and other tissues in diabetes/ obesity, the heart and vessels cardiovascular diseases, brain in Alzheimer's disease, around cancers, bone in osteoporosis and osteoarthritis, kidney in renal disease, and liver in cirrhosis and steatosis in preclinical species and humans, all conditions that are associated with physical dysfunction (frailty), hyperinflammation Cytokine storm), and CoV morbidity and mortality.

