Based upon review of the published literature and our pre-clinical data, we do not anticipate the occurrence of serious adverse events with the prescribed regimen in this study. We have identified a variety of drug-drug interactions (*e.g.*, current use of warfarin) for which we established exclusion criteria or modification plans to minimize associated risks. We could find no reports of Fisetin toxicity in the literature. Some flavonols have been associated with DNA damage *in vitro*, but Fisetin exerts little or no genotoxic effects. To the contrary, Fisetin has been noted to be anticarcinogenic. Indeed, we found that chronic Fisetin administration delays cancer in mice and increases remaining lifespan in old mice as well as increasing lifespan of DNA damage/ genotoxicity highly-prone  $Ercc1^{-/\Delta}$  mice by over  $17\%^{59}$ . Since up to 50% of most mouse strains die from cancers, this shows that the beneficial effects of Fisetin on such procarcinogenic factors as senescent cell burden and tissue chronic inflammation appear to more than counteract any theoretical effects of flavonol-associated genotoxicity. **Fisetin actually reduces cancer risk**, as opposed to increasing it.

Overall, we do not anticipate substantial risk from the natural product, Fisetin, which is present in many foods, including cucumbers, strawberries, and other fruits and vegetables, albeit at levels lower than will be used here. CoV infection causes 25 to 50% mortality in nursing home patients. Thus, the risks of using this drug are likely minimal compared to the anticipated benefits for nursing home patients with a limited life expectancy, even without CoV infection.

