# 8 Statistical Plan

### 8.1 Sample Size Determination

Power calculations for the comparison of the Fisetin and control groups were made assuming an equal distribution among the 7-point scale categories at Day 14 among the controls using a two-sided significance level of 0.05 (alpha). With 75 subjects per group, the study would have 80% power to detect a log odd's ratio of 0.81 which translates to an odd's ratio of 2.25 comparing the control to Fisetin group. Power calculations were run using the PASS software package.

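### Kaplan-Meier rates and medians are planned for non-fatal events with no rule for death; if deaths are censored, as is the default, the event proportions are overstated

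*Combined protocol and SAP*

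**What the plan says.** The secondary endpoint part of Section 8 (8.2.1 in the contents list) gives one set of methods for all time-to-event endpoints. Of the endpoints it says: "These include time to hospital discharge, survival, or symptom improvement". Of the method: "Kaplan-Meier methods will be used to graphically evaluate potential differences between treatment arms or other groups of interest". The same curves are to supply medians and time-specific rates, with the example "rate of transfer to hospital at 14 days". Cox models compare the arms. Time to oxygen supplementation or intubation is to be handled in a similar way, as exploratory work.

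No censoring rule is given for any of these endpoints. Competing risks, cumulative incidence and composites that include death are not mentioned.

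Three other places bear on how death would be treated:

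- Section 3.3 follows each subject for up to six months or until death.
- Section 4.4.4 counts death as a form of withdrawal.
- Section 8.2 carries last known values forward to Day 180 for early withdrawals who received some treatment. It does so in the paragraph on the primary ordinal analysis.

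On how common death may be, Section 1.6 says "CoV infection causes 25 to 50% mortality in nursing home patients", and Section 1.1 gives the same range. Section 8.1 plans the sample size "assuming an equal distribution among the 7-point scale categories at Day 14 among the controls".

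**The concern.** Death rules out a later transfer, discharge or improvement. A Kaplan-Meier curve that censors at death treats a person who died as someone who could still have the event. Its complement then describes a hypothetical setting without death, not the share of participants who have the event. Whenever deaths come before later events, that complement lies above the true share.

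Three results are at stake: the absolute rates, the medians, and the between-arm differences read from the curves. The differences matter most if Fisetin changes mortality, because the gap between the two quantities then differs by arm. The protocol describes a population with substantial mortality and makes death a category of its primary scale, so deaths before the event are to be expected.

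**Working it through.** **1. The plan's own figure.** No rate, event count or power is stated for a time-to-event endpoint. The one calculated design figure is in Section 8.1: "With 75 subjects per group, the study would have 80% power to detect a log odd's ratio of 0.81". Seven equal control categories with OR 2.25 give Fisetin proportions 0.273, 0.201, 0.154, 0.122, 0.099, 0.082 and 0.069. The cubes of the arm-averaged proportions sum to 0.024. By the Whitehead formula V = 150 × (1 − 0.024)/12 = 12.20, and power = Φ(ln 2.25 × √12.20 − 1.96) = Φ(0.87) = 80.9%. The stated power reproduces, which supports reading the assumption as 1/7 = 14.3% of controls dead at Day 14.

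**2. Inputs for the bias.** Let p be the true proportion with the event in the window and d the proportion who die first. The documents give no p, so 20%, 40% and 60% are assumptions. For d, 14.3% is the planning value, and 25% and 50% are the ends of the background range, which carries no time window. Taking every death as coming before the event is the worst case at each mortality level.

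**3. Formula, constant cause-specific hazards.** Total cumulative hazard H = −ln(1 − p − d). The event's share is H × p/(p + d). With deaths censored, 1 − KM = 1 − exp(−H × p/(p + d)).

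Example: p = 0.20, d = 0.143. H = −ln(0.657) = 0.420; share = 0.420 × 0.583 = 0.245; 1 − exp(−0.245) = 0.217.

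| True event proportion | Deaths first | 1 − KM reads |
|---|---|---|
| 20% | 14.3% | 21.7% |
| 40% | 14.3% | 43.8% |
| 60% | 14.3% | 66.6% |
| 20% | 25% | 23.3% |
| 60% | 25% | 73.8% |
| 20% | 50% | 29.1% |
| 40% | 50% | 64.1% |

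For scale, the binomial standard error with 75 per arm is √(0.2 × 0.8/75) = 4.6 points at 20% and √(0.6 × 0.4/75) = 5.7 points at 60%. At the planning mortality the bias is 1.7 and 6.6 points respectively.

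**4. Medians.** Take discharge among hospitalised participants, with the total hazard set to 1. If 25% die in hospital, the KM median is ln 2/0.75 = 0.92, while half are truly discharged only at −ln(1 − 0.5/0.75) = 1.10. If 50% die in hospital, cumulative incidence never reaches one half, yet KM still gives a median of ln 2/0.5 = 1.39.

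**5. Arm differences.** Assume 30% control transfer, a cause-specific hazard ratio of 0.7 for transfer and 0.5 for death.

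- With 14.3% control deaths first, the KM difference is 8.5 points and the true incidence difference 6.8.
- With 25% control deaths first, they are 9.0 and 5.9 points.
- With equal transfer hazards, the death hazard halved and 25% control deaths first, KM shows 35.3% in both arms. True incidence is 30.0% in control and 32.5% on Fisetin.

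**The case against.** **Censoring at death is never stated.** This is correct; it is inferred from Sections 3.3 and 4.4.4 and from standard practice. If the carry-forward rule in Section 8.2 reached these endpoints, treated participants who died would stay in the risk set and 1 − KM would be close to cumulative incidence. But that rule concerns values in the primary analysis and is not extended to event times. It does not fill the gap.

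**The background mortality is the wrong yardstick at 14 days.** This largely stands. The 25–50% figure has no time window and counts all deaths, including those after a transfer, which do not compete with it. A reader might infer that 14-day transfer would be overstated by half. At the plan's own Day 14 assumption, 20% becomes 21.7%. The larger figures need mortality well above that value, or a common event.

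**The Cox model is sound.** This stands. With deaths censored it validly estimates a cause-specific hazard ratio. A reader might conclude that Cox is wrong for everything except survival, but that does not follow. The ratio simply does not describe absolute risk on its own.

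**Extra deaths need not flatter an arm.** A reader might infer that an arm with more early deaths would look better on time to improvement. Under the constant-hazard model the KM curve depends only on the event hazard, so extra deaths leave it unchanged. A reversal needs dependent censoring, with those who die also being those least likely to improve. The documents give no figures for that.

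**Little rests on these curves.** This is fair. The endpoints are secondary or exploratory, the primary scale ranks death as its worst category, and Section 8 also plans crude proportions. With complete follow-up, though, the crude 14-day proportion and the KM rate for the same event would disagree in one report.

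**Conclusion.** The point holds in limited form. The plan takes Kaplan-Meier rates and medians for non-fatal events, gives no rule for death, and by default would censor it. The reported proportions would then be too high. At the plan's implied 14.3% mortality the excess is 1.7 points at a true 20%, 3.8 at 40% and 6.6 at 60%. With 25% deaths it is 3.3 points at 20% and 13.8 at 60%. The 50% case is an outer bound. KM differences between arms depart from incidence differences when mortality differs by arm.

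These sizes rest on constant hazards, assumed event rates and all deaths preceding the event. The direction of the bias rests only on deaths being censored and some of them coming first. Survival, the primary analysis, the crude proportions and the sample size are not affected. The change should be made, but the trial's main conclusion does not depend on it.

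**What to change.** In the secondary endpoint part of Section 8:

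- State a rule for death for each time-to-event endpoint, separately from the rule for loss to follow-up and withdrawal of consent.
- For transfer, discharge, symptom improvement, and start of oxygen or intubation, estimate rates and medians by Aalen-Johansen cumulative incidence with death as a competing event. Report the median as not reached if incidence stays below one half.
- Keep the Cox model. Label its result a cause-specific hazard ratio, and show the cause-specific hazard ratio for death and the death curve beside it.
- Gray's test is optional. If used, note that lower mortality can by itself raise the cumulative incidence of a non-fatal event, as in the 30.0% against 32.5% example.
- Keep Kaplan-Meier for survival.

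The cost is a few sentences and standard software. Follow-up to death is already planned, so no new data are needed and the sample size does not change.

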# 9 Safety and Adverse Events

Safety evaluations will include adverse event (AE) and serious AE (SAE) reporting. Adverse event reporting will be conducted throughout the study for all subjects. The reporting period begins at the time of informed consent and continues through study completion. Adverse events will be assessed at every visit by study or nursing home staff.

Definitions, documentation, and reporting of AEs are described in Section 9.1-9.4.

#### 9.1 Definitions

9.1.1 Unanticipated Problems Involving Risk to Subjects or Others (UPIRTSO) Any unanticipated problem or adverse event that meets the following three criteria:

- Serious: Serious problems or events that result in significant harm (which may be physical, psychological, financial, social, economic, or legal), or increased risk for the subject or others (including individuals who are not research subjects). These include: (1) death; (2) life threatening adverse experience; (3) hospitalization inpatient, new, or prolonged; (4) disability/incapacity persistent or significant; (5) breach of confidentiality, and (6) other problems, events, or new information (*i.e.* publications, DSMB reports, interim findings, product labeling change) that in the opinion of the local investigator may adversely affect the rights, safety, or welfare of the subjects or others, or substantially compromise the research data, **AND**
- Unanticipated: (*i.e.* unexpected) problems or events are those that are not already described as potential risks in the protocol, consent document, not listed in the Investigator's Brochure, or not part of an underlying disease. A problem or event is "unanticipated" when it was unforeseeable at the time of its occurrence. A problem or event is "unanticipated" when it occurs at an increased frequency or at an increased severity than expected, **AND**
- Related: A problem or event is "related" if it is possibly related to the research procedures.

#### 9.1.2 Adverse Event

An Adverse Event (AE) is any untoward or medical occurrence in a patient or clinical investigation subject administered a study product and which does not necessarily have a causal relationship with this treatment. Therefore, an AE is any unfavorable and unintended sign (including abnormal laboratory finding), symptom, or disease, which is temporarily associated with the use of an investigational product in a patient or research subject, whether or not considered related to the investigational product.

An AE also includes any worsening (ie, any clinically significant change in frequency and/or intensity) of a pre-existing condition that is temporarily associated with the use of the study drug.

#### 9.1.3 Serious Adverse Event

Adverse events are classified as serious or non-serious. Serious problems/events can be well defined and include:

- Death includes all deaths, even those that appear to be completely unrelated to study drug (eg, a car accident in which a patient is a passenger).
- Life threatening adverse experience in the view of the investigator, the patient is at immediate risk of death at the time of the event. This does not include an AE that had it occurred in a more severe form, might have caused death
- Hospitalization Inpatient hospitalization is defined as admission to a hospital or an emergency room for longer than 24 hours. Prolongation of existing hospitalization is defined as a hospital stay that is longer than originally anticipated for the event or is prolonged due to the development of a new AE, as determined by the investigator or treating physician.
- Inpatient, new, or prolonged; disability/incapacity.
- Persistent or significant disability or incapacity.
- Birth defect/congenital anomaly.

and/or *pe*r protocol may be problems/events that in the opinion of the sponsor-investigator may have adversely affected the rights, safety, or welfare of the subjects or others, or substantially compromised the research data.

All adverse events that do not meet any of the criteria for serious will be regarded as **non-serious adverse events**.

Criteria for reporting SAEs must be followed for these events. See section regarding reporting of SAEs for more information on recording and reporting SAEs.

All study subjects will be provided with study team contact information 24/7. They will be educated on contacting the study team if any of these events occur. This will allow the study staff to be contacted if a serious adverse event occurs between study visits.

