## 2 Study Objectives

#### 2.1 Primary Objectives

The primary objective is to test the efficacy of the senolytic drug (Fisetin) in preventing or delaying progression of CoV severity in nursing home patients with proven CoV according to a 7 point scale for nursing home CoV severity adapted from the WHO Ordinal Scale for Clinical Improvement of CoV\*:

- Not hospitalized nor on additional oxygen (compared to baseline), at baseline level of function (as assessed by activities of daily living).
- Not hospitalized nor on additional oxygen, but below previous level of function.
- Hospitalized or moved to a more intensive unit within the nursing home because of additional dysfunction (not simply because of positivity), but not requiring additional oxygen nor placed on an antiviral drug for worsening CoV symptoms.
- Hospitalized or moved to a more intensive unit within the nursing home and requiring additional oxygen (vs. baseline) and/ or placed on an antiviral drug for worseningCoV symptoms.

- Hospitalized or moved to a more intensive unit within the nursing home and requiring additional oxygen by ECMO or ventilator.
- Transferred to palliative care to provide end-of-life care.
- Death.

\*The WHO Ordinal Scale for Clinical Improvement of CoV (Appendix 1) is scored from 0 to 8 with 0 = no evidence of infection to 8 = death. Our adapted scale does not include scores 0 or 1, since no subjects in COVID-FIS will meet these criteria (e.g., all subjects have proven CoV infection, so none have "no infection").

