# 3.5 Secondary Study Endpoints

In this pilot study of elderly adults in nursing homes who have proven CoV infection and no, mild, or moderate symptoms (Table 4), secondary endpoints will be: 1) safety and tolerability; 2) decreased blood senescent cells (blood CD3+ T cell assay for p16INK4A and SASP factors; if feasible); 3) cognitive function (from MDS section C, Cognitive Patterns, items C0100 – C1310; 4) function status/activities of daily living (from MDS Section G, Functional Status, items G0110-G0900; 5) functional abilities/frailty (from MDS section GG, Functional Abilities and Goals, items GG0130-0170 improved physical and cognitive function; 6) decreased circulating inflammatory markers and mediators (if feasible); 7) prevention or delay of deterioration in oxygenation status (SpO2/FiO2) if feasible; 8) reduced progression to intubation/ transition to end-of-life palliative care because of worsening condition, transfer to special nursing home unit admission because of worsening condition, hospital, ICU admission/ progression to ARDS/ myocarditis with troponin leak, death, delayed recovery, and delayed antibody response, and 9) decreased lung fibrosis during or at the end of the 6 month time subjects are in the study.

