# 3.6 Primary Safety Endpoints

The primary safety endpoints are incidence of serious adverse events and hypersensitivity reactions. Safety assessments are undertaken with the measurement of safety laboratory tests and procedures, vital signs, and recording of adverse events.

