# 9.1.9 Hospitalization, Prolonged Hospitalization, or Surgery

Any adverse event that results in hospitalization or prolonged hospitalization will be documented and reported as a serious adverse event unless specifically instructed otherwise in this protocol. Any condition responsible for surgery will be documented as an adverse event if the condition meets the criteria for an adverse event.

Neither the condition, hospitalization, prolonged hospitalization, or surgery will be reported as an adverse event in the following circumstances:

The following hospitalizations will not be considered SAE for this study:

- a visit to the emergency department or other hospital department <24 hours, that does not result in admission (unless considered an important medical or life-threatening event).
- elective surgery planned prior to signing consent.
- admissions as *per* protocol for a planned medical/surgical procedure.
- routine health assessment requiring admission for baseline/trending of health status (*e.g.*, routine mammogram).
- medical or surgical admission other than to remedy ill health and planned prior to entry into the study. Appropriate documentation will be obtained in these cases.

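### Section 9.1.3 recognises escalation of care only as hospital or emergency-room admission and lists no important-medical-event criterion, so some events managed in the nursing home's intensive unit are classed as non-serious

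*Combined protocol and SAP*

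**What the plan says.** Section 3.6 sets the endpoint: "The primary safety endpoints are incidence of serious adverse events and hypersensitivity reactions".

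Section 9.1.3 lists what makes an event serious: death, a life-threatening event, hospitalization, persistent or significant disability or incapacity, and birth defect. Hospitalization is defined by place and, on one reading, by length of stay: "Inpatient hospitalization is defined as admission to a hospital or an emergency room for longer than 24 hours". A closing clause allows further events that, in the sponsor-investigator's opinion, may have harmed rights, safety or welfare. Everything else has a default: "All adverse events that do not meet any of the criteria for serious will be regarded as" non-serious.

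Section 9.1.9 makes any adverse event that results in hospitalization an SAE and states no minimum stay. It excludes visits of under 24 hours that do not end in admission, with the exception "unless considered an important medical or life-threatening event".

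The primary efficacy scale in section 2.1 treats the two places of care as equal. Counting its categories in list order:

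- Level 3: "Hospitalized or moved to a more intensive unit within the nursing home because of additional dysfunction (not simply because of positivity"
- Level 4: "Hospitalized or moved to a more intensive unit within the nursing home and requiring additional oxygen (vs. baseline"
- Level 5: "Hospitalized or moved to a more intensive unit within the nursing home and requiring additional oxygen by ECMO or ventilator"

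Section 3.5 also counts "transfer to special nursing home unit admission because of worsening condition" within its eighth secondary endpoint.

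**The concern.** For efficacy, the protocol accepts that a resident who worsens may be escalated inside the home instead of being sent to hospital, and it scores the two alike. For safety, only the second counts as escalation. Two residents with the same deterioration can then differ on a primary safety endpoint because one home has a higher-care unit and the other does not.

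The label has consequences. The 24-hour notice to the sponsor-investigator and the five-working-day IRB report in section 9.3 start from an event identified as serious. FDA reporting in 9.4 covers serious suspected reactions. Section 9.8 names an excessive number of SAEs as a ground on which the DSMB may recommend stopping. A drug effect managed in place could reach these channels late or not at all.

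**Working it through.** **No plan figure to correct.** The documents give no SAE rate, no power for SAE incidence and no share of deteriorations managed in the home. The power statement in 8.1 does reproduce: by the proportional-odds formula, log OR 0.81 with controls spread equally over seven categories needs 73.5 per group and gives 80.8% power at 75. It says nothing about SAEs. The point rests on reading the definitions together.

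**Step 1: one event, two places.** Take a level 3 or 4 deterioration that is not fatal, does not put the resident at immediate risk of death and leaves no persistent or significant disability.

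| Test | Admitted to hospital | Moved to the home's intensive unit |
|---|---|---|
| Scale level (2.1) | 3 or 4 | 3 or 4 |
| Hospitalization (9.1.3, 9.1.9) | met | not met |
| Death, life-threatening, disability (9.1.3) | not met | not met |
| Important medical event | not needed | not listed in 9.1.3 |
| Sponsor-investigator opinion (9.1.3) | not needed | possible, discretionary |
| Result by rule | SAE | non-serious unless the opinion clause is used |

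**Step 2: which levels are exposed.** Level 5 involves a ventilator or ECMO and would usually meet the life-threatening criterion wherever managed. The exposed group is mainly levels 3 and 4.

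**Step 3: the opinion clause.** Under 9.3.1 the sponsor-investigator reviews all adverse event reports, so non-serious events are seen. The stated purpose is to decide on FDA reports. No step for reclassifying an event and no deadline is given. The site investigator, who is closest to the event, has no equivalent clause in 9.1.3, although the UPIRTSO definition in 9.1.1 gives the local investigator one.

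**Step 4: the 24-hour wording.** If the 24 hours in 9.1.3 qualify both hospital and emergency room, an admission of under 24 hours fails 9.1.3 but is an SAE under 9.1.9. If they qualify only the emergency room, the two sections agree on admissions. The text does not settle which is meant.

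**Step 5: direction of effect, on assumed inputs only.** Suppose 40% against 20% of residents have a qualifying deterioration, with 75 per arm and two-sided 0.05. Let q be the share managed in the home and r the share of those caught by another criterion, both equal in the two arms. The captured fraction is 1 − q + qr. With p̄ the mean of the two rates,

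power = Φ{[|p1 − p2| − 1.96·√(2p̄(1 − p̄)/75)] / √([p1(1 − p1) + p2(1 − p2)]/75)}.

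For q = 0.5 and r = 0: captured fraction 0.5; rates 0.20 and 0.10; p̄ = 0.15; the two standard errors are 0.0583 and 0.0577; power = Φ[(0.10 − 1.96 × 0.0583)/0.0577] = Φ(−0.25) = 0.40.

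| q | r | Captured | Observed rates | Power |
|---|---|---|---|---|
| 0 | any | 1 | 40% vs 20% | 77% |
| 0.25 | 0 | 0.75 | 30% vs 15% | 60% |
| 0.5 | 0.5 | 0.75 | 30% vs 15% | 60% |
| 0.5 | 0 | 0.5 | 20% vs 10% | 40% |
| 0.75 | 0 | 0.25 | 10% vs 5% | 21% |
| any | 1 | 1 | 40% vs 20% | 77% |

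The ratio of rates stays at 2 throughout; the counts, the absolute difference and the power fall. None of these inputs comes from the documents. The table shows the mechanism, not an estimate.

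**The case against.** The strongest reply is that the information is not lost, only the label. In-home transfers and the ordinal score are recorded daily if feasible (3.1, 7.3), transfer for worsening is part of secondary endpoint 8, event endpoints are compared by arm (8.2), and the events remain AEs. The DSMB sees unblinded data on outcomes and safety, not SAE counts alone. The review and hold rule in 9.6 is worded on severe events, and severity in 9.3.3 is graded without reference to place of care. Only directly related SAEs and UPIRTSOs go to the IRB under 9.3.1, so most COVID-19 progression would not be reported there under either definition. An efficacy scale that groups levels of care need not define seriousness, and making every in-home step-up an SAE would turn much of the efficacy outcome into SAEs in both arms and could dilute a drug signal.

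Most of this stands. It limits the harm and rules out an automatic SAE for every transfer. It does not remove the gap: SAE incidence is a named primary safety endpoint, the 24-hour notice depends on the label, and an event serious only through hospitalization loses that label when managed in the home.

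Three stronger readings are tempting and unsupported. A reader might infer that deteriorations managed in the home are simply absent from SAE incidence; fatal, life-threatening and disabling events count wherever managed, and the opinion clause can add others. A reader might infer that a resident must be away for more than 24 hours; 9.1.9 sets no minimum stay for an admission. A reader might infer bias between arms; randomization balances use of in-home units in expectation, and bias would need treatment to influence where residents are managed.

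**Conclusion.** The gap is real but narrow. An event managed in the home's intensive unit, mainly at levels 3 and 4, that is not fatal, life-threatening or disabling is non-serious by a stated rule unless the sponsor-investigator uses a discretionary clause. The same event in hospital is an SAE. The result is under-counting, lower sensitivity of the SAE endpoint and later notification.

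Its size cannot be computed from the documents. A reader might take the equal control distribution in 8.1, put 3/7 = 43% of controls at levels 3 to 5, assume 25% to 75% are managed in the home, and arrive at 11% to 32% of controls; leaving out level 5 gives 2/7 = 29%, and 7% to 21%. Neither range is an estimate. The distribution is a power assumption about status at Day 14, not an incidence of adverse events; the in-home share is invented; and the sum ignores the disability and opinion routes.

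The conclusion assumes that some participating homes manage such events in place, which the scale's own wording anticipates.

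**What to change.** 1. Add to the list in 9.1.3: an important medical event in the judgment of the site investigator, wherever managed. Section 9.1.9 already presupposes the concept.
2. Reconcile the 24-hour wording of 9.1.3 with 9.1.9, so that both say whether the 24 hours apply to hospital admissions or only to emergency-room stays.
3. Do not make every in-home transfer an automatic SAE. Add a case report form prompt for the site investigator to assess seriousness at each transfer to a more intensive unit for worsening.
4. Tabulate those transfers by arm beside SAE incidence, using data already collected for secondary endpoint 8.

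The cost is a short amendment to 9.1.3 and 9.1.9, one form prompt, one table and some more SAE reports, many probably from COVID-19 progression in both arms.
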